7.2. Classification of AE/ADEs

A medically-qualified investigator must assess all AEs in terms of causal relationship to intervention, severity, and "expectedness" using the following guidelines.

Not related	There is not a reasonable causal relationship to the investigational product and the adverse event.
Unlikely related	No temporal association or the cause of the event has been identified, or the drug or device is unlikely to be implicated, but there is a low likelihood that a causal relationship exists.
Possibly related	There is reasonable evidence to suggest a causal relationship between the drug and adverse event.
Related	There is evidence to suggest a causal relationship, and the influence of other factors is unlikely.

Classification of Adverse Events Regarding Severity Scale

1	Mild AE: Awareness of sign, symptom, or event, but easily tolerated; no treatment required
2	Moderate AE: Discomfort enough to cause interference with usual activity and may warrant intervention. In the latter scenario, AE responds to treatment
3	Severe AE: Incapacitating, limiting usual/normal activities or significantly affects clinical status requiring hospitalization or prolongation of hospitalization.
4	Life-threatening or disabling
5	Fatal AE

Expectedness: The expectedness of an AE/ADE or SAR shall be determined according to the specified reference document containing safety information (e.g., most current investigator's brochure or product label). Any AE/ADE that is not identified in nature, severity, or specificity in the current study reference document(s) (e.g. protocol or investigator's brochure) is considered unexpected. Events that are mentioned in the investigator's brochure as occurring with a class of drugs or as anticipated from the pharmacological properties of the drug, but not specifically mentioned as occurring with the particular drug under investigation, are considered unexpected.

The following AEs are expected, disease-related events in patients with HF with preserved ejection fraction (HFpEF).

- 1. Unplanned hospitalization, ER visit or clinic visit for worsening HF
- 2. Arrhythmias, particularly atrial fibrillation
- 3. Sudden cardiac death
- 4. Acute coronary syndrome
- 5. Cerebrovascular event
- 6. Venous thromboembolism
- 7. Lightheadedness
- 8. Worsening renal function
- 9. Shortness of breath at rest or during/after exercise
- 10. Fatigue at rest or during/after exercise

The following are potential expected side effects of KNO₃:

- 1. Stomach discomfort
- 2. Slight headache
- 3. Dizziness

- 4. New onset or worsening lightheadedness
- 5. Low blood pressure
- 6. Stomach ache, diarrhea, nausea, or vomiting
- 7. Worsening shortness of breath
- 8. Worsening fatigue
- 9. Flushing
- 10. Rash
- 11. Mild orthostatic hypotension

Clinically significant methemoglobinemia or significant symptomatic orthostatic hypotension (20 mmHg or greater reduction in systolic blood pressure with associated symptoms such as dizziness upon standing) are potential expected side effects to KNO₃, although we will consider them unexpected given prior data in this patient population with this particular drug and dosing scheme.

The following are potential expected side effects of regadenoson administration (for subjects participating in the cardiac MRI sub-study):

- 1. Headache
- 2. Dizziness
- 3. Nausea or stomach discomfort
- 4. Decreased sense of taste
- 5. Mild chest discomfort
- 6. Shortness of breath
- 7. Flushing (warmth, redness, or tingly feeling under the skin)

These side effects are transient and generally resolve upon clearance of the drug and/or reversal of drug effects with dypiridamole.

The following are potential expected side effects of gadolinium-based contrast administration (for subjects participating in the cardiac MRI sub-study):

- 1. Injection site pain (from the needle)
- 2. Burning at injection site (if the dye contacts the skin)
- 3. Headache
- 4. Dizziness or faintness
- 5. A decrease in blood pressure
- 6. Nausea
- 7. Vomiting
- 8. Sweating
- 9. Paresthesias

These side effects occur in a small minority of patients, but if they do occur they will be noticed within minutes of the injection and are transient in nature.

7.3. Recording and Reporting of Adverse Events

The site PIs will continuously supervise all aspects of the trial and review the records of the study subjects following each visit and at the end of their participation. The site PIs will be responsible

for ensuring that all adverse events are noted, followed and reported to the Sponsor database and IRB as per local requirements.

SAEs occurring from the time of *signed informed consent* to the Week 15 phone visit will be captured on a CIOMS form. AEs will be classified according to the guidelines/definitions specified in section 7 of the protocol. Any AE rated >=3 in severity and all SAEs must be reported by the site investigator or qualified designee within 1 working day of first becoming aware of the event, to the Sponsor via email (at [contact]), and the medical director ([name]), with CC to the study chair ([name]). The IRB should be notified as per institutional guidelines at each respective site. The medical director will make an immediate determination about the necessity to modify the protocol, include additional information in the consent form, inform previous participants, temporarily hold enrollment of patients, or terminate the study.

The investigator or qualified designee will enter the required information regarding the AE into the appropriate module of the eCRF, All study procedures and cumulative adverse events are subject to full IRB review at least yearly and DSMB review every 6 months.

Events significant enough to necessitate modification of study drug dosing will be captured on an appropriate eCRF module ("Study Drug Dosing" page). Should the PI determine that a modification to study drug is appropriate, the PI must obtain written approval from the Sponsor to proceed with this exception to the protocol.

7.4. Follow-up

The Investigator will record follow-up safety information according to the same process used for reporting the initial event as described above. The Investigator will follow all safety events until resolution, stabilization or the event is otherwise explained.

The DSMB will review detailed safety data approximately every 6 months throughout the study, as detailed in the Data Safety Monitoring Section of this protocol and in the Data Safety Monitoring Charter.

7.5. Management of Suspected Unexpected Serious Adverse Reaction

AEs that meet the criteria of serious, related to study intervention, and unexpected for the study intervention, qualify for expedited reporting by the Sponsor to the regulatory authorities. The Site Investigator will assess all SAEs occurring at his/her site and evaluate for "unexpectedness" and relationship to study drug. The Site Investigator is required to complete a report for any event identified as serious, study drug related and unexpected, using the CIOMS format, and to submit it to the Sponsor within 1 working day of the PI or site personnel being aware of it. The sponsor will submit a safety report according to regulations.

A copy of the report sent by the PI to the Sponsor should be kept at the site Regulatory Binder

7.6. Pregnancy

Pregnancy is a contraindication to enrollment in the study. Pregnancy occurring during the study period, although not considered an SAE, must be reported to the Sponsor within the same

timelines as an SAE, and to the IRB per local requirements. The pregnancy will be recorded on the appropriate note to file. The drug will be discontinued immediately and subject terminated from the trial, but the pregnancy will be followed until final outcome. Any associated AEs or SAEs that occur to the mother or fetus/child will be recorded in the AE or SAE case report form.

8. STUDY MEASUREMENTS AND DATA COLLECTION

8.1. Assessment of exercise capacity

We will use a supine bicycle exercise protocol in conjunction with expired gas analysis to assess oxygen consumption (VO₂) during exercise. Subjects will perform a maximal exertion limited exercise test using a graded-exercise protocol. We will use a supine cycle ergometer designed for stress echocardiography (Stress Echo Ergometer 1505, Medical Positioning, Inc, Kansas City, MO). Subjects will undergo expired gas analysis with a Parvo Medics True One 2400 device (Parvo Medics, Sandy, UT), an Innocor device (Innovision Inc) or equivalent. Resistance began at 15 W for 3 minutes, increasing to 25 W for 3 minutes, and then increasing by 25 W every 3 minutes thereafter. Breath-by-breath information will be recorded. We will use custom-designed software already developed in Matlab (MathWorks, Natick, MA) at our lab for offline processing and quantification of all exercise data.¹¹¹ All data quantification will be blinded to treatment. Total work performed will be computed and exercise efficiency will be defined as (total work/total oxygen consumed). Exercise efficiency is not a formal endpoint of the trial, but will be used to interpret changes in the co-primary outcomes.

8.2. Quality of life assessment

[figure not shown]
This will be assessed with the Kansas City Cardiomyopathy Questionnaire (KCCQ).¹²⁴ We will administer the KCCQ to subjects prior to randomization and at the end of each intervention phase (6-week time point in both phases). This is a validated 23-item questionnaire that assess physical function, symptoms, social function, self-efficacy and knowledge, and quality of life. It has been used extensively in heart failure studies (http://cvoutcomes.org/pages/3214).

8.3. Assessment of the systemic vasodilatory response to exercise

Blood pressure will be measured with a validated oscillometric device at rest, at each stage of exercise and after exercise. Cardiac output will be measured at rest and at each stage of exercise using echocardiography. Systemic vascular resistance (SVR) will be calculated at rest and at peak exercise as mean arterial pressure / cardiac output. Systemic vasodilatory reserve will be measured as the reduction in SVR during exercise, relative to SVR at rest ([rest SVR– peak exercise SVR] / rest SVR).¹¹¹ Depending on equipment availability at each site, we may also monitor and record muscle oxygenation in the calf (lateral aspect of left gastrocnemius) and forearm (flexor digitorum superficialis) during exercise non-invasively using a Portamon or Portalite near-infrared spectroscopy device (Artinis Medical Systems; The Netherlands). Both the Portamon and Portalite are investigational devices and not currently approved medical devices in the U.S.

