Based on preliminary data demonstrating the effects of a single oral dose of inorganic nitrate in HFpEF, the current trial was designed to assess the efficacy of sustained oral administration of inorganic nitrate in a more diverse and representative sample of HFpEF patients and to further assess the mechanisms by which inorganic nitrate enhances oxygen uptake and exercise capacity. This is a randomized double-blind crossover clinical trial, in which 84 subjects with HFpEF will receive the following 2 interventions, in randomized order: (1) Potassium nitrate (KNO₃), at a dose of 12-18 mmol/d by mouth for approximately 6 weeks, or; (2) Potassium chloride (KCI), at a dose of 12-18 mmol/d by mouth for approximately 6 weeks. A 1-week washout period will be introduced between the 2 interventions. The purpose of the trial is to test the efficacy of KNO₃ on a number of clinical and physiologic endpoints in subjects with HFpEF.

Our specific aims are:

Specific Aim 1: To assess whether KNO₃ therapy improves endpoints with direct clinical relevance: aerobic capacity and quality of life (QOL).

Hypothesis 1a: KNO_3 will improve exercise capacity, quantified as: (1) Total work performed during a maximal-effort exercise test; (2) Peak oxygen consumption (VO₂) during a symptom-limited maximal effort exercise test. These will be the co-primary endpoints of the trial.

Hypothesis 1b: KNO_3 will improve QOL, assessed using the Kansas City Cardiomyopathy Questionnaire.

Specific Aim 2: To dissect the effects of KNO₃ on specific physiologic adaptations to exercise

Hypothesis 2a: KNO₃ improves the systemic vasodilator response to exercise, measured as the change in systemic vascular resistance during a symptom-limited maximal effort exercise test.

Hypothesis 2b: KNO₃ improves muscle blood flow during exercise, measured with flowsensitive PC-MRI during a standardized plantar flexion exercise test.

Hypothesis 2c: KNO₃ improves muscle Cr recovery kinetics (a marker of oxidative capacity), measured with MRI. We will also assess the exercise-induced spatial matching (i.e., within muscle) of blood flow and oxidative capacity using a highly novel method (chemical exchange saturation transfer) that allows, for the first time, for highresolution spatial mapping of Cr in muscle.

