 To assess whether KNO₃ improves quality of life To assess whether KNO₃ improves the systemic vasodilator response to exercise To assess whether KNO₃ improves muscle blood flow during exercise. To assess whether KNO₃ improves muscle PCr recovery kinetics (a marker of oxidative capacity) To assess whether KNO₃ improves LV diastolic function and myocardial systolic strain To assess whether KNO₃ reduces late systolic LV load from wave reflections
 To assess whether KNO₃ improves the exercise-induced spatial matching (i.e., within muscle) of blood flow and oxidative capacity (assessed by chemical exchange saturation transfer). To assess whether KNO₃ has different effects in men vs. women and in African-American vs. non-African American subjects To assess whether KNO₃ improves: Ventilatory threshold, VO₂ kinetics

• Natriuretic peptide levels

	 Physical activity (measured via accelerometry) 24-hour late systolic pressure augmentation, measured with the Aurora device
	4. To assess the relationship between nitrate and nitrite levels achieved and the therapeutic response achieved in each subject (improvement in endpoints in response to KNO ₃ vs. placebo)
Primary Endpoint	Total work performed and peak oxygen uptake (VO₂) during a symptom-limited maximal effort exercise test after approximately 6 weeks of KNO ₃ vs. KCI.
Secondary Endpoints	 Quality of life score, assessed using the Kansas City Cardiomyopathy Questionnaire.
	 The change in systemic vascular resistance reserve during exercise during a symptom-limited maximal effort exercise test.
	 Muscle blood flow during exercise, measured with flow sensitive PC- MRI during a standardized plantar flexion exercise test.
	4. The time constant of Cr recovery after a plantar flexor exercise protocol.
	 Measures of LV diastolic function (E/e', left atrial volume index) and peak global systolic myocardial longitudinal and circumferential strain.
	6. Augmentation index, late systolic wall stress and aortic input impedance.

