3.5.1. Changes in exercise capacity and oxygen uptake: Nitrate supplementation resulted in a greater peak VO₂ (12.6±3.7 versus 11.6±3.1 mL O₂/kg/min; *P*=0.005) and total work performed (55.6±35.3 vs. 49.2±28.9 kJ; *P*=0.04). Ventilatory threshold (a marker of the cellular anaerobic threshold) was greater following NO₃- supplementation (7.6±1.8 versus 7.0±1.4 mL O₂/kg/min, P=0.03). Because total work performed and O₂ consumption increased in tandem, exercise efficiency was no different. This is interestingly, different than the effect seen in athletes and younger subjects, among whom exercise efficiency increases^{70, 103-107}, demonstrating the importance of characterizing specific adaptations to exercise in this particular patient population.

3.5.2. Exercise vasodilatory reserve: NR-BRJ led to a significant fall in systemic vascular resistance (SVR) at peak exercise (-42±17%) compared to PB (-32±20%; P=0.03). This was accompanied by an increase in cardiac output (% change in NR-BRJ 122±60 vs PB: 89±53%, P=0.006), increased heart rate (78.0±24.1 versus 65.6±21.0%, P=0.001) and a trend towards greater stroke volume (22.6±22.4 versus 12.7±25.4%, P=0.13).

3.5.3. Effects on filling parameters: Interestingly, we found no evidence of reduced preload, since end-diastolic volume (EDV) significantly increased with beetroot supplementation (112±12 mL vs 93±6 mL; P=0.04), whereas the E/E' ratio did not change (NR-BRJ: 12.1±0.9 vs. PB: 11.5±0.8; P=0.90). The increased LV EDV may suggest improvements in diastolic function, which we plan to further assess in this proposal using measurements of intraventricular pressure gradients.

**3.5.4.** Augmentation index: The aortic Alx (derived from radial tonometry) was significantly decreased by NO₃- supplementation (NO₃- 132.2 \pm 16.7 versus PB 141.4 \pm 21.9%, P=0.03).

(mean arterial pressure change=0.17 mmHg; systolic BP change=0.7 mmHg; both P>0.85) with NO₃⁻ supplementation. This is in contrast to BP-lowering effect in healthy volunteers and drug naïve hypertensive subjects^{112, 113} and likely explained by recent data indicating that the BPlowering effect of inorganic nitrate is mediated by its renal effects in pathways downstream of the AT1-receptor.¹¹⁴ These effects are likely attenuated in patients who are treated with ACE inhibitors/angiotensin receptor blockers for BP control (such as occurs in HFpEF patients).

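### The vasodilator endpoint takes SVR at each period's own peak, so it cannot separate a direct vascular effect of KNO3 from the effect of exercising further

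*Combined protocol and SAP*

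**What the plan says.** Hypothesis 2a in Section 1 is that KNO3 improves the systemic vasodilator response to exercise, "measured as the change in systemic vascular resistance during a symptom-limited maximal effort exercise test". The synopsis lists the measure as secondary endpoint 2. Section 8.3 gives the formula: "Systemic vasodilatory reserve will be measured as the reduction in SVR during exercise, relative to SVR at rest", that is, (rest SVR − peak SVR) / rest SVR. Only two time points enter: "Systemic vascular resistance (SVR) will be calculated at rest and at peak exercise as mean arterial pressure / cardiac output".

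The same section collects more than the endpoint uses. On pressure: "Blood pressure will be measured with a validated oscillometric device at rest, at each stage of exercise and after exercise". On output: "Cardiac output will be measured at rest and at each stage of exercise using echocardiography". Section 8.1 fixes the workload steps: 15 W for 3 minutes, 25 W for 3 minutes, then 25 W more every 3 minutes.

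No section defines SVR at a matched stage, workload or VO2. Section 10.2 names period, sequence and a random subject effect for the mixed model, plus baseline outcome and covariates found prognostic. It does not name achieved workload. It also plans an exploratory structural equation model linking treatment, mechanistic variables and clinical variables.

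**The concern.** Section 3.2 says that afterload has to fall during exercise as cardiac output rises, if arterial pressure is not to climb too far. A subject who goes further in one period may therefore show a lower SVR at the end of that test with no direct drug effect on the vessels.

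The trial expects exactly this imbalance, because greater total work and peak VO2 on KNO3 are the co-primary hypotheses. When the drug succeeds on those, the vasodilator endpoint compares unequal intensities, and the bias runs in favour of Hypothesis 2a.

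What is at stake is the reading of Aim 2a as a mechanism. The structural equation model inherits the problem: its mechanism variable may partly be a result of the clinical variable that it is meant to explain.

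**Working it through.** **Inputs from the documents.** Pilot results (Sections 3.5.1 and 3.5.2), nitrate versus control:
- peak VO2 12.6 vs 11.6 mL/kg/min
- total work 55.6 vs 49.2 kJ
- rise in cardiac output (CO) 122% vs 89%
- SVR: a "significant fall in systemic vascular resistance (SVR) at peak exercise (-42±17%) compared to PB (-32±20%; P=0.03"

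Section 10.1 gives a design gain of 0.6 mL/kg/min, a standardized effect of 0.49, 90% retention of 84 subjects, and a detectable change in vasodilatory reserve of 8.2%, read here as percentage points. No SD for reserve and no stage-level SVR is given, so the 8.2% cannot be reproduced and the size below is an extrapolation.

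**Assumptions.** Resting VO2 r = 2.5 to 4.0 mL/kg/min. The CO increment is proportional to the VO2 increment. There is no direct vascular effect.

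**Step 1, control-period ratios.** CO peak/rest = 1.89 and SVR peak/rest = 1 − 0.32 = 0.68. Since SVR = MAP/CO, MAP peak/rest = 0.68 × 1.89 = 1.285.

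**Step 2, carry the control period to a higher peak.** For a gain g in peak VO2:
- k = (11.6 + g − r) / (11.6 − r)
- CO ratio = 1 + 0.89k
- reserve with the MAP ratio fixed = 1 − 1.285 / (1 + 0.89k)
- reserve with MAP scaled too = 1 − (1 + 0.285k) / (1 + 0.89k)

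Subtracting the control reserve of 32% leaves the part due to effort alone:

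| Gain g | r | k | CO ratio | MAP fixed | MAP scaled |
|---|---|---|---|---|---|
| 0.6 (design) | 2.5 | 1.066 | 1.949 | +2.1 points | +1.1 points |
| 0.6 (design) | 4.0 | 1.079 | 1.960 | +2.4 points | +1.3 points |
| 1.0 (pilot) | 2.5 | 1.110 | 1.988 | +3.3 points | +1.8 points |
| 1.0 (pilot) | 4.0 | 1.132 | 2.007 | +4.0 points | +2.1 points |

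The range is 1.1 to 2.4 points at the design gain and 1.8 to 4.0 at the pilot gain. The pilot difference was 42 − 32 = 10 points. If SVR has already levelled off before peak, the figure tends to zero.

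**Step 3, effect on the test of this endpoint.** The evaluable number is 84 × 0.9 ≈ 76. Two SDs of the paired difference are tried:
- 8.2 / 0.49 = 16.7 points
- 8.2 / 0.326 = 25.2 points, where 0.326 is the standardized effect that a paired t-test detects with 80% power at n = 76

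With noncentrality (shift/SD) × √76 and two-sided α of 0.05, a shift of 1.1 to 2.4 points with no direct vascular effect would be declared significant 9% to 24% of the time (SD 16.7) or 7% to 13% (SD 25.2), instead of 5%.

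**Step 4, how far apart the pilot peaks were.** With work as power × time, cumulative work is 2.7, 7.2, 16.2, 29.7, 47.7 and 70.2 kJ at the ends of the 15, 25, 50, 75, 100 and 125 W stages. Both pilot means lie in the 125 W stage: (49.2 − 47.7)/0.125 = 12 s in on control and (55.6 − 47.7)/0.125 = 63 s in on nitrate.

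**The case against.** **The pilot does not show a workload artefact.** A reader might note that the implied MAP ratios are almost equal (0.68 × 1.89 = 1.285 on control, 0.58 × 2.22 = 1.288 on nitrate) and infer that the whole 10-point difference came from exercising further. That does not follow. Because SVR = MAP/CO, higher output at equal pressure is lower SVR by identity, and a true vasodilator would give the same pattern. Effort scaling at the pilot gain predicts an 11% to 13% larger CO rise, whereas the observed rise was 122/89 = 1.37 times as large. This objection stands.

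**The intensities may differ little.** The pilot means fall within one stage, about 51 seconds apart, so many subjects may have the same last stage in both periods. This also stands for the means. The SDs of total work are large (35.3 and 28.9 kJ), so individuals will differ.

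**Peak reserve is a legitimate measure.** It matches the pilot definition and the 8.2% power statement. The plan's hypothesis is that nitrite is converted to NO preferentially in hypoxic muscle, so a submaximal stage may miss the effect where it should be largest. This argues against replacing the endpoint, but not against adding a matched analysis.

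**Other cover and status.** Muscle flow during standardized plantar flexion does not depend on the cycling peak, but it is local, done only if feasible, and not done at Northwestern. Section 10.2 describes the secondary aims as exploratory. Both points limit the importance of the problem without removing it.

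**Conclusion.** The point holds as a limit on interpretation. As defined, the endpoint cannot separate better vasodilation from exercising further, and nothing else in the plan makes that separation for SVR. The possible contribution of effort is about 1.1 to 2.4 points at the design gain and 1.8 to 4.0 at the pilot gain. These figures rest on ratios of group means, an assumed resting VO2 and proportional cardiac output, and they shrink to nothing if SVR plateaus before peak.

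A reader might infer that any larger SVR fall on KNO3 will be false. The documents do not support that: better vasodilation may itself be why subjects do more work, and no stage-level SVR is given to settle the direction. The co-primary analyses are not touched.

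**What to change.** Keep SVR reserve at peak as secondary endpoint 2. Before unblinding, add to Sections 8.3 and 10.2 a companion analysis: the fractional fall in SVR from rest to the highest stage the subject completed in both periods, analysed with the same mixed model. State how subjects with no common completed stage are handled. Say in Section 10.2 that Aim 2a will be interpreted as a direct vasodilator effect only if the matched-stage result supports it. Run the exploratory structural equation model with the matched-stage value as well as the peak value.

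No new measurement is needed; the cost is the added text and analysis. The drawback is that the matched stage is submaximal for some subjects, so the effect there may be smaller. The 8.2% detectable change applies only to the peak version, so the detectable change for the companion should be stated separately, or its absence acknowledged.
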